#### 8.4.2 UNANTICIPATED PROBLEM REPORTING

The investigator will report unanticipated problems or events as outlined in the Safety Management Plan. The unanticipated problem report will include the following information:

- Protocol identifying information: protocol title and number, Principal Investigator's name, and the IRB project number
- A detailed description of the event, incident, experience, or outcome
- An explanation of the basis for determining that the event, incident, experience, or outcome represents an unanticipated problem
- A description of any changes to the protocol or other corrective actions that have been taken or are proposed in response to the unanticipated problem

To satisfy the requirement for prompt reporting, unanticipated problems will be reported using the following timeline:

- Unanticipated problems that are SAEs will be reported to the IRB and to the study Sponsor within 24 hours of the investigator becoming aware of the event.
- Any other unanticipated problem will be reported to the IRB and to the study Sponsor within 7 days of the investigator becoming aware of the problem.
- All unanticipated problems should be reported to appropriate institutional officials (as required by an institution's written reporting procedures), the supporting agency head (or designee), and the OHRP within 10 days of the IRB's receipt of the report of the problem from the investigator.

An investigator shall submit to the Sponsor and to the reviewing IRB a report of any unanticipated adverse device effect occurring during an investigation as soon as possible, but in no event later than 10 working days after the investigator first learns of the effect (21 CFR 812.150(a)(1)). A Sponsor who conducts an evaluation of an unanticipated adverse device effect under 812.46(b) shall report the results of such evaluation to the FDA and to all reviewing IRB's and participating investigators within 10 working days after the Sponsor first receives notice of the effect. Thereafter the Sponsor shall submit such additional reports concerning the effect as FDA requests (21 CFR 812.150(b)(1)).

---

#### 8.4.3 REPORTING UNANTICIPATED PROBLEMS TO PATIENTS

Not applicable.

## 9 STATISTICAL CONSIDERATIONS

### 9.1 STATISTICAL HYPOTHESES

There are no formal study hypotheses to be tested in this study. We hypothesize that no safety concerns are revealed in eyes receiving LL-BMT1.

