### 2.3 POTENTIAL RISKS AND BENEFITS TO HUMAN PATIENTS

Adverse reactions of greatest concern reported with bimatoprost eyedrops include pigmentation (including blepharal pigmentation and iris hyperpigmentation), eyelash changes, intraocular inflammation, macular edema, and hypersensitivity. In controlled clinical trials, the most common adverse reaction was conjunctival hyperemia (31%). Approximately 1.6% of patients discontinued therapy due to conjunctival hyperemia. Other adverse drug reactions (reported in 1% to 4% of patients) with Lumigan® 0.01% included conjunctival edema, conjunctival hemorrhage, eye irritation, eye pain, eye pruritus, erythema of eyelid, eyelids pruritus, growth of eyelashes, hypertrichosis, instillation site irritation, punctate keratitis, skin hyperpigmentation, vision blurred, and visual acuity reduced. In post-marketing use, AEs reported also include asthma-like symptoms, dizziness, dry eye, dyspnea, eye discharge, eye edema, foreign body sensation, headache, hypersensitivity (including signs and symptoms of eye allergy and allergic dermatitis), lacrimation increased, and periorbital and lid changes (including deepening of the eyelid sulcus; Lumigan PI).

The bimatoprost in LL-BMT1 is printed on Group 4 extended-wear contact lenses. Risks to patients in the present study are those typical of contact lenses.

The potential benefit to patients in this study is the lowering of IOP without the use of daily eyedrops.

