### 4 STUDY DESIGN

#### 4.1 OVERALL DESIGN

This will be an open-label, phase 2a clinical study. Five patients with treated or treatment-naïve POAG or OHT in both eyes will be enrolled. All previously treated eyes will have a washout period prior to enrollment. At least one eye (called the study eye) will have untreated (after washout, if applicable) IOP between 22 mmHg and 34 mmHg (inclusive). If both eyes meet this criterion, then the eye with the higher IOP will be selected as the study eye. If the IOP in both qualified eyes is the same, then the right eye will be selected as the study eye. If the fellow eye does not meet this IOP criterion, it must have an untreated IOP (following washout, if applicable) within 5 mmHg of the study eye without exceeding the 34-mmHg maximum. For all enrolled patients, both eyes will be treated, and all tests will be performed separately on both eyes, but only the study eye will be included for efficacy analysis.

Beginning 2 weeks prior to the Baseline Visit, all patients will have a 2-week run-in acclimation period with a nonmedicated contact lens in each eye to ensure contact lens tolerability. The patient will be questioned about AEs related to the contact lens wear. The patient must have experienced no contact lens-related AEs in order to be eligible for the study. If a patient does not successfully complete the 2-week acclimation screening, that patient will be replaced until at least 5 patients successfully complete the acclimation screening. Those patients who have completed acclimation screening will be enrolled as patients for dosing with LL-BMT1. After insertion of the LL-BMT1 (medicated) lens, patients will be followed for 7 or 8 days for assessments of safety and IOP reduction.

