#### 8.3.4 TIME PERIOD AND FREQUENCY FOR EVENT ASSESSMENT AND FOLLOW-UP

Any medical condition that is present at the time that the patient is screened will be considered as medical history and not reported as an AE. However, if the study patient’s condition deteriorates at any time after enrollment, it will be recorded as an AE.

Changes in the severity of an AE will be documented to allow an assessment of the duration of the event at each level of severity to be performed. AEs characterized as intermittent require documentation of onset and duration of each episode.

The investigator or qualified designee will record all reportable events with start dates occurring any time after informed consent is obtained until 7 days (for non-serious AEs) or 30 days (for SAEs) after the last day of study participation. Patient will be told to call and notify the investigator of such events that occur during this period after the end of study visit. Events will be followed for outcome information until resolution or stabilization.

AEs will be monitored throughout the study beginning at the time the patient signs the informed consent for this study. At each post-Baseline visit, the investigator will begin by querying for AEs by asking each patient a general, non-directed question, such as “How have you been feeling since the last visit?” Directed questioning and examination will then be done as appropriate. All reported AEs will be documented on the appropriate eCRF, including seriousness, severity, relationship to study drug, action taken, and outcome (including date of resolution or stabilization, if AE is not ongoing). If AEs occur, the first concern will be the safety of the study patients.

If a patient becomes pregnant during the study, the investigator must inform the Sponsor and collect follow-up data regarding the pregnancy, birth, and status of the child. The Sponsor will provide special CRFs for data collection in the case of pregnancy. Follow-up should be continued until study close-out at the study center. After close-out, the Sponsor's Safety designee will continue to obtain follow-up information. Pregnancy should be recorded as a protocol deviation. Pregnancy is not an AE; however, any complication related to pregnancy would be considered an AE.

---

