## 9.2 SAMPLE SIZE DETERMINATION

Due to the exploratory nature of this study, no formal power sample size calculation has been performed. An empirical sample size of at least 5 evaluable patients is planned. Assuming a 10%-20% drop-out non-evaluable rate, up to 7 patients (7 study eyes) will be consented to begin acclimation screening. Those who are consented but fail acclimation screening will be replaced until at least 5 patients successfully complete the acclimation screening. Five patients who pass acclimation screening will be enrolled as patients for study treatment.

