### 9.4.2 SAFETY ANALYSES

Analysis of treatment-emergent AEs will be conducted based on the safety population. Safety endpoints include:

- AEs
- Concomitant medications
- Heart rate and blood pressure
- BCVA
- IOP
- Biomicroscopy
- Conjunctival hyperemia

Ocular events will be reported on an eye level, while non-ocular events will be on a patient level.

AEs will be coded using the Medical Dictionary for Regulatory Activities (MedDRA). For each AE reported, the number and percent of patients/eyes will be tabulated based on the preferred term and ocular and non-ocular AEs will be reported separately. The tables will be generated by relationship to treatment as well as by system organ class and severity.

The primary safety endpoint is the AE rate ( $100 \times [\text{number of AEs} / \text{number of eyes exposed to treatment}]$ ). The modified safety set will be used for a sensitivity analysis of the primary safety endpoint.

*Secondary safety endpoints:*

- Percent of patients with  $\geq 5$ -mmHg increase from baseline in IOP at each visit
- Abnormal slit-lamp biomicroscopy findings at the Baseline, Day 1, and Day 7 Visits
- Contact lens protein deposits at the Day 7 Visit
- Change from baseline in CLDEQ-8 results at the Day 7 Visit

Pre-existing AEs, those identified after enrollment but before treatment with LL-BMT1, will be tabulated for all consented patients.

---

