5 STUDY VARIABLES/PARAMETERS

5.1 Primary Endpoints

The primary safety endpoint is the adverse event (AE) rate, defined to be $100 \times [\text{number of AEs} / \text{number of eyes exposed to treatment}]$.

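### The primary AE rate divides all AEs by exposed eyes, so it does not show how many of the 5 patients were affected; no any-AE patient count or interval is planned

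*Protocol*

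**What the plan says.** Protocol 9.4.2 states: "The primary safety endpoint is the AE rate", and gives it as 100 times the number of AEs over the eyes exposed. SAP 5.1 repeats this ("The primary safety endpoint is the adverse event (AE) rate"), with the denominator "number of eyes exposed to treatment". SAP 6.7 gives the formula again, in a section whose primary analysis is of treatment-emergent AEs. None of the three places limits the numerator to ocular events, or to first events per patient or eye.

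On numbers, Protocol 9.2 says: "Five patients who pass acclimation screening will be enrolled as patients for study treatment". Protocol 4.1 says: "For all enrolled patients, both eyes will be treated".

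Protocol 9.4.2 also sets a unit of reporting: ocular events by eye, non-ocular events by patient. It plans counts and percentages of patients or eyes by preferred term, with tables by relationship, system organ class and severity. The SAP does not repeat these tables. It declares no changes from the protocol (SAP 1.1), so they are not withdrawn.

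No interval is named for any safety summary. SAP 6 lists descriptive statistics only, and the 95% level in Protocol 9.4.1 is attached to exploratory tests.

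Protocol 9.1 says that nothing will be formally tested, then adds: "We hypothesize that no safety concerns are revealed in eyes receiving LL-BMT1". The synopsis (Protocol 1.1) states the same hypothesis without the disclaimer. Neither place says what would count as a concern.

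**The concern.** The primary objective is safety in patients, so the headline figure should let a reader see how many patients had a problem. A count of AEs over a count of eyes does not do that. For non-ocular events the denominator is twice the number of people at risk and departs from the protocol's own reporting unit. For all events, the rate does not separate one patient with several AEs from several patients with one each.

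The counting rule is also incomplete. Protocol 8.3.4 says "AEs characterized as intermittent require documentation of onset and duration of each episode", but neither document says whether such an AE enters the numerator once or once per episode. In an open-label study that should be settled before the data are seen.

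The informal hypothesis then stands beside a headline number with no statement of precision. The stake is interpretation: a low rate could be read as more reassuring than 5 patients allow, and a high one could reflect a single patient.

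**Working it through.** **Inputs.** Patients treated: 5 (Protocol 9.2). Eyes per patient: 2 (Protocol 4.1). Exposed eyes: 5 × 2 = 10, assuming both lenses are inserted in every patient. Rate = 100 × AEs / eyes (Protocol 9.4.2, SAP 5.1).

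**The plan's own figure.** The only derived number is up to 7 consented, for 5 evaluable after 10%–20% loss. 5/(1 − 0.10) = 5.56, rounded up to 6; 5/(1 − 0.20) = 6.25, rounded up to 7. It reproduces. There is no power or precision figure to check.

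**What the rate identifies.** If k patients each have one non-ocular AE, the rate is 100k/10 = 10k, while the percentage of patients affected is 100k/5 = 20k. The rate is half the patient percentage.

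| Hypothetical data | AEs | Rate per 100 eyes | Patients affected | Exact 95% CI, patients |
|---|---|---|---|---|
| One non-ocular AE in each of 5 patients | 5 | 50 | 5/5 (100%) | 47.8%–100% |
| Four AEs, all in one patient | 4 | 40 | 1/5 (20%) | 0.5%–71.6% |
| One AE in each of four patients | 4 | 40 | 4/5 (80%) | 28.4%–99.5% |

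The last two rows have the same primary result. The intervals are Clopper-Pearson; for 5/5 the lower limit is 0.025^(1/5) = 0.478.

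**What 5 patients can exclude.** For zero affected out of n, the exact upper limit is 1 − (α/2)^(1/n) two-sided, or 1 − α^(1/n) one-sided.

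- 0/5, two-sided 95%: 1 − 0.025^(1/5) = 52.2%.
- 0/5, one-sided 95%: 1 − 0.05^(1/5) = 45.1%.
- 0/4, two-sided 95%: 1 − 0.025^(1/4) = 60.2%. This can arise because patients who leave after enrolment are not replaced (Protocol 5.5 and 7.2).
- 0/10, two-sided 95%: 1 − 0.025^(1/10) = 30.8%. This would apply only if the two eyes of a patient were independent, so it should not be used.

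**Chance of seeing no case.** With true patient risk p, P(0 of 5) = (1 − p)^5. Protocol 2.3 gives rates for bimatoprost eyedrops. Applying them to one week of lens wear is an assumption, so a range is shown.

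| Assumed risk | Basis | P(0 of 5) |
|---|---|---|
| 31% | conjunctival hyperemia, eyedrops | 15.6% |
| 10% | illustrative | 59.0% |
| 4% | top of the 1%–4% group, eyedrops | 81.5% |
| 1.6% | discontinuation for hyperemia, eyedrops | 92.3% |
| 1% | bottom of the 1%–4% group, eyedrops | 95.1% |

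**The case against.** The strongest reply is that the study claims little. Protocol 4.1 and 9.1 and SAP 6 disclaim formal testing, Protocol 9.2 calls the study exploratory, and no threshold or decision uses the AE rate. An event rate over eyes is openly defined, and preferring incidence is partly a matter of choice. Protocol 9.4.2 already plans patient and eye counts by preferred term, and Protocol 9.4.7 plans line listings for each patient. With 5 patients, a reader of those outputs could see who had what.

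Much of this stands. It makes the point one of reporting rather than a failed design. It does not remove it: counts by term cannot simply be added up to the number of patients with any AE, no interval accompanies them, and the headline endpoint still departs from the protocol's own unit for non-ocular events.

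The documents do not support three stronger readings that a reader might infer:

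- **That the per-eye metric causes the limit of about 50%.** It does not. The limit comes from having 5 patients and stays the same under any metric.
- **That each episode of an intermittent AE counts separately,** so that seven episodes in one eye would give 100 × 7/10 = 70. Protocol 8.3.4 is a documentation instruction, and one AE with several recorded episodes is its natural reading. The documents are silent on counting.
- **That the sponsor will conclude safety from a clean result.** No passage says so. The sentence in Protocol 9.1 is informal.

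**Conclusion.** The point holds as a low-cost improvement to the primary summary. As written, the primary AE rate does not identify patient risk: the same value of 40 covers 1 or 4 of 5 patients affected, and a value of 50 can mean that all 5 are. There is no overall count of patients with any treatment-emergent AE and no interval, while the synopsis and Protocol 9.1 carry an informal hypothesis with no definition of a concern.

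Separately, zero affected patients would leave true risks up to 52% (two-sided) or 45% (one-sided) open.

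The rate examples assume 10 exposed eyes. The limits assume 5 evaluable patients with independent outcomes. The chances of seeing no case rest on eyedrop rates that may not apply here: Protocol 4.3 puts the lens's 7-day release at about 25% of the eyedrop total, and Protocol 2.3 gives no exposure time for its rates. The conclusion about the metric does not depend on those rates.

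**What to change.** - **SAP 5.1 and 6.7:** lead with the number and percent of patients with at least one treatment-emergent AE, as three rows (any, ocular, non-ocular), each with an exact Clopper-Pearson 95% CI at patient level.
- **Counting rule:** count each preferred term once per patient, or once per eye in eye-level ocular tables. State whether an intermittent AE enters the event count once or once per episode.
- **Event rate:** keep it as a supporting figure, with ocular events over exposed eyes and non-ocular events over patients. Do not attach a binomial interval to it, since it is not a proportion.
- **Protocol 1.1 and 9.1:** replace the hypothesis with what the study can state, namely that no event in 5 patients excludes only true risks above about 45% (one-sided) to 52% (two-sided). Recompute the limit if fewer than 5 are evaluable.
- **Any comparison with the eyedrop rates in Protocol 2.3:** label it as an assumption.

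The data are already to be collected, so no visits or patients are added. The cost is a few lines of wording, a small addition to one table and a more modest conclusion.

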## 9.2 SAMPLE SIZE DETERMINATION

Due to the exploratory nature of this study, no formal power sample size calculation has been performed. An empirical sample size of at least 5 evaluable patients is planned. Assuming a 10%-20% drop-out non-evaluable rate, up to 7 patients (7 study eyes) will be consented to begin acclimation screening. Those who are consented but fail acclimation screening will be replaced until at least 5 patients successfully complete the acclimation screening. Five patients who pass acclimation screening will be enrolled as patients for study treatment.

## 9.3 POPULATIONS FOR ANALYSES

The following populations will be analyzed:

- Safety population: Includes all patients whose eyes are in contact with LL-BMT1 lenses.
- Intent-to-treat (ITT) population: Includes all patients who have LL-BMT1 lenses successfully inserted.
- Modified intent-to-treat (mITT) population: Includes all patients who have LL-BMT1 lenses successfully inserted and complete at least 1 on-therapy follow-up assessment; only the study eye from each patient will be included in this analysis.

## 9.4 STATISTICAL ANALYSES

### 9.4.1 GENERAL APPROACH

The database will be locked after all patients exit the study and all data clarification forms or queries have been resolved. Prior to database lock, a detailed Statistical Analysis Plan (SAP) will be finalized and approved. Final analysis will occur after database lock.

Wherever appropriate, summary statistics will include the frequency, mean, standard deviation, median, minimum, and maximum for continuous and ordinal variables, and frequency counts and percent for categorical variables. Graphical representations of the results may also be provided.

In general, unless otherwise specified, eyes will be the analytical unit and a formal statistical test will only be conducted for exploratory purposes when sample size is deemed appropriate. All testing will be two-sided with a 95% confidence level. Due to the small sample size in this study, nonparametric approach will be applied. For quantitative variables, within-eye before-and-after comparisons will be assessed using one-sample Wilcoxon test. For qualitative variables, Fisher's Exact test will be used.

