#### 9.4.3 EFFICACY ANALYSES

The secondary efficacy endpoint is the change from baseline in IOP at each visit.

The efficacy analyses will be based on the mITT population and only the study eyes will be used. Statistical analyses will be performed using methods described in Section 9.4.1.

---

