6.8 Secondary Analysis

There will be both safety and efficacy assessments in the secondary analysis.

The secondary safety analysis will consist of identifying the following:

- Percent of patients with ≥ 5 mmHg increase from baseline in IOP at each visit
- “Abnormal” and “Severe” slit-lamp biomicroscopy findings at the Baseline, Day 1, and Day 7 Visits
- Contact lens protein deposits at the Day 7 Visit
- Change from Baseline in CLDEQ-8 results at the Day 7 Visit

The secondary efficacy analysis will consist of identifying the change from baseline in IOP at each visit. Study eyes only within the modified intent-to-treat population will be used for this part of the analysis.

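### With the eye as default unit, any exploratory test on ocular safety data would count 5 correlated pairs of eyes as 10 independent observations

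*Protocol*

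**What the plan says.** Protocol 9.4.1 sets the default: unless specified otherwise, "eyes will be the analytical unit". It then assigns a one-sample Wilcoxon test to before-and-after changes within an eye and Fisher's exact test to qualitative variables, two-sided at the 95% level. The same section limits formal tests to exploratory use, and only if the sample size is judged adequate. It gives no criterion for that judgement.

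Protocol 4.1 states: "For all enrolled patients, both eyes will be treated, and all tests will be performed separately on both eyes". Five patients therefore supply up to 10 eyes.

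Some analyses have their own unit:
- **Efficacy.** Protocol 4.1 says "only the study eye will be included for efficacy analysis". Protocol 9.4.3 and SAP 6.8 agree: "The efficacy analyses will be based on the mITT population and only the study eyes will be used" and "Study eyes only within the modified intent-to-treat population will be used for this part of the analysis".
- **Adverse events.** Protocol 9.4.2: "Ocular events will be reported on an eye level, while non-ocular events will be on a patient level".
- **IOP rise.** The endpoint is a percentage of patients (Protocol 9.4.2, SAP 5.2 and 6.8).
- **CLDEQ-8.** One form is completed per patient (Protocol section 12).

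SAP section 6 lists descriptive statistics, states that no hypotheses are tested, and names no test and no unit. SAP 1.1 declares no changes from the protocol, so the 9.4.1 default and its tests still stand.

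**The concern.** Two eyes of one person share the systemic, behavioural and measurement conditions of that person, so their changes are usually correlated. Neither document mentions this correlation, clustering, or a patient-level summary for ocular safety data. The plan uses one eye per patient for efficacy but gives no equivalent rule for BCVA, biomicroscopy, conjunctival hyperemia, or IOP summarised as a safety variable.

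If the 9.4.1 tests are applied to those variables, 10 eyes enter as if they came from 10 people. The p-values are then too small, and any SE or confidence interval added at reporting is too narrow. Safety is the primary objective, and the open-ended sample-size condition adds to the exposure, because counting 10 eyes rather than 5 patients can itself make a test look justified.

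**Working it through.** **The plan's own figure.** There is no power calculation. The one figure is up to 7 consented for 5 evaluable at 10% to 20% loss (Protocol 9.2, SAP 3.1). 5/0.90 = 5.56, rounded up to 6; 5/0.80 = 6.25, rounded up to 7. It reproduces. The units are 5 patients and 5 × 2 = 10 eyes.

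**Inputs.** Two-sided 0.05 and the one-sample Wilcoxon test come from Protocol 9.4.1. The documents give no inter-eye correlation of change (ρ), so ρ is an assumption and a range is shown.

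**Size of the 10-eye test under independence.** The exact test rejects when the smaller rank sum is 8 or less. The number of sign patterns with rank sum 0, 1, …, 8 is 1+1+1+2+2+3+4+5+6 = 25, so the size is 2 × 25/1024 = 0.0488.

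**Closed forms for 5 pairs with equal variance σ².**
- Var(mean of 10 eyes) = σ²(1+ρ)/10, so true SE / naive SE = √(1+ρ) with σ taken as known, and effective n = 10/(1+ρ).
- E[s²] = σ²(1 − ρ/9), so the SD is about √(1 − ρ/9) of its true value.

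**Simulation.** 200,000 runs per value of ρ; 5 bivariate normal pairs with no true change, analysed as 10 independent eyes.

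| Assumed ρ | Wilcoxon type I error | True / naive SE | Effective n | Coverage of nominal 95% t interval | SD relative to truth |
|---|---|---|---|---|---|
| 0 | 4.9% | 1.00 | 10.0 | 95.0% | 1.00 |
| 0.3 | 8.2% | 1.14 | 7.7 | 91.5% | 0.98 |
| 0.5 | 11.0% | 1.22 | 6.7 | 88.6% | 0.97 |
| 0.7 | 13.9% | 1.30 | 5.9 | 85.4% | 0.96 |
| 0.9 | 17.1% | 1.38 | 5.3 | 81.6% | 0.95 |

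**Other scales.** Further simulations used 20,000 runs, ρ from 0.5 to 0.9, and the exact test with zero changes dropped.
- BCVA in whole letters (SD of change 4 letters, assumed): type I error roughly 9% to 16%, close to the normal case.
- Three-level changes (worse, same, better) standing in for graded slit-lamp scores: about 3% to 7% if half the changes are zero, and about 1% to 2% if 70% are zero. The share of zeros is an assumption.

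**Results that need no assumed ρ.**
- Smallest possible two-sided exact Wilcoxon p: 2/2⁵ = 0.0625 on 5 patients, against 2/2¹⁰ = 0.002 on 10 eyes. The choice of unit alone decides whether p below 0.05 is attainable.
- Upper limit of a two-sided 95% exact interval after zero events: 1 − 0.025^(1/5) = 52.2% on 5 patients, against 1 − 0.025^(1/10) = 30.8% on 10 eyes taken as independent.

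**The case against.** The strongest reply is that the plan is descriptive. Protocol 4.1 and 9.1 and SAP section 6 disclaim formal hypotheses, 9.4.1 makes tests optional, and the SAP names none. No SE or confidence interval is listed anywhere, and the primary AE rate has neither an interval nor a test. The only section that points back to the 9.4.1 methods is Efficacy (9.4.3), which has no pairs. Protocol 9.4.2 names no test for safety. All of this stands, and it limits the severity.

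A reader might infer that every reported spread, or the primary result itself, is wrong. The documents do not support that. The planned measure of spread is the SD, which pairing lowers by only about 2% to 5% over the range shown. The SE factors of 1.14 to 1.38 apply to a quantity that is not planned. A reader might also apply the 8% to 17% range to slit-lamp grades; with many zero changes the inflation is small or absent.

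It can also be said that a patient-level test is no use at n=5, since it cannot reach 0.05. That is true and should be disclosed. It supports reading these data descriptively and does not justify doubling the count. Likewise, a two-eye mean is not a free choice: Protocol 6.2.1 and 7.1 let a patient continue with one lens, so a mean could mix a treated and an untreated eye.

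What the reply does not remove is that 9.4.1 still authorises these tests with the eye as unit, and SAP 1.1 leaves it unchanged.

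**Conclusion.** The point holds, with low to moderate impact. As written, 9.4.1 would give anti-conservative p-values for near-continuous ocular safety variables (BCVA, IOP as a safety variable) if its optional tests were run on both eyes. True type I error would be about 8% to 17% against a nominal 5%, under normally distributed changes and assumed inter-eye correlations of 0.3 to 0.9. Any interval added on 10 eyes would under-cover in the same way.

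Not affected are the secondary efficacy analysis, the IOP-rise percentage, CLDEQ-8 and non-ocular AEs. The AE rate per eye exposed, being descriptive, is affected only if an interval or test is attached to it. No planned primary or secondary summary is shown to be wrong.

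**What to change.** In Protocol 9.4.1 and SAP section 6, state that:
1. Eye-level tables of ocular safety data are descriptive only.
2. Ocular findings are also shown as the number of patients with at least one affected eye, out of 5.
3. Any exploratory test, SE or confidence interval uses one value per patient, named in advance. The study eye is the natural choice because it matches the efficacy analysis.
4. With 5 patients the smallest two-sided exact Wilcoxon p is 0.0625, so no such test can reach 0.05 and the results are read descriptively.

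In the same edit, reconcile the tonometry text in Protocol 8.2, which averages the two eyes to obtain each patient's change in IOP, with the study-eye rule in Protocol 4.1 and 9.4.3 and SAP 6.8.

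The cost is wording only, using data already collected. The price is that significance at 5% is given up for these variables and any interval becomes wider. The fellow eye is left out of tests but stays in the descriptive tables.
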